6.3.13.3 Blood pressure and heart rate measurements

Pre-clinical investigations have included a recent dog telemetry study which demonstrated small, transient decreases in blood pressure, left ventricular systolic pressure, cardiac contractility and relaxation indices, as well as increases in heart rate, at blood concentrations about 5 times higher than the maximum dose used in this study (ie, 25 mg). The clinical significance of this finding is uncertain and follow-up preclinical testing is underway in telemetered dogs with lower doses of NKTR-118. While there have been isolated reports of patients with potentially clinically significant blood pressure decreases in trials of NKTR-118, such cases have also been observed with placebo. No clear or consistent cardiovascular signal has been observed in human studies to date.

Therefore, care should be taken in the measurement of heart rate and blood pressure at all visits; for specific instructions on methods for measurement, please refer to Section 6.3.12.1. For specific instructions regarding the potential need for discontinuation based on sustained clinically significant vital sign abnormalities, please refer to Section 5.8. It should be noted that vital sign abnormalities should generally be reported as AEs only if they fulfill AE criteria proper or are the reason for discontinuation of treatment with the IP (see Section 6.3.4).

In general, the investigator should maintain a low threshold for considering additional diagnostic tests (eg, ECGs, echocardiogram, additional orthostatic measurements, chest x-rays, etc.) as appropriate, based on clinical assessment and patient history.

6.3.14 Safety specific areas of interest

Specific safety topics of interest for this trial include, but are not limited to, the following:

- Opioid withdrawal
- Abuse liability
- Bowel perforation type events (eg, ischemic colitis) (See Section 6.3.13.2)
- Cardiovascular type events (including, but not limited to, abnormalities in blood pressure and heart rate)

The topics listed above, as well as other topics which may be subsequently determined by AstraZeneca, will be subject to enhanced surveillance activities. Furthermore, an adjudication committee will independently assess certain of these areas of interest (ie, bowel perforation type events, cardiovascular type events, etc.). Additionally, the topics above will be analyzed for presentation in the CSR in accordance with the Statistical Analysis Plan (SAP).

Additionally, routine safety monitoring and patient risk management processes as outlined in AstraZeneca clinical trial standard operating procedures (SOPs) and in the Patient Risk Management Plan (PRMP) will be carried out to protect patients in clinical studies with NKTR-118.

6.4 Patient reported outcomes (PROs)

The following PRO is utilized in this study:

6.4.1 NRS

See Section [6.3.7](#).

6.4.2 Administration of PRO questionnaire

The NRS (for pain) will be self-administered at the study center. All patients will be instructed to answer the questions on their own, without help from others (family, friends, or study staff). In addition, for visits after randomization (Visit R1), the questionnaire is to be filled out at the start of the relevant visits, prior to any investigations or discussions about patients' symptoms with the study staff. An exception to this is made for the randomization visit, since only randomized patients will fill out the questionnaire and interaction with study staff will be necessary to determine whether randomization criteria have been met.

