- Complete physical examination (including rectal examination) for rollover patients (Note: this will be obtained from last visit of the previous NKTR-118 study, but must also include rectal examination). New patients will have a targeted physical examination (lungs, cardiovascular, abdomen) with weight. Special emphasis should be placed on the pre-randomization abdominal examination so as not to

enroll any patients with an acute abdominal process (see Section 4.2). At the discretion of the investigator, a rectal examination may also be performed for new patients, if necessary to ensure the safety of the patient.

- Pain level question (NRS) (average pain over the previous 7 days) will be completed.
- Sitting blood pressure and pulse must be measured (obtained from last visit of the previous NKTR-118 study for rollover patients). Please see Section 6.3.12.1 for additional details on the protocol-mandated methods for collection of vital signs. The accurate time in date, hours and minutes will be recorded for this measurement.
- 12-lead ECG after resting for 10 minutes, with triplicate ECGs collected over a 5-minute period. (obtained from last visit of the previous NKTR-118 study for rollover patients)
- Urine sample will be collected for urine pregnancy test (WOCBP). The urine pregnancy test result must be negative before the patient may continue with the visit and administration of study drug. Patients enrolling from a previous study will also have U/A and urine drug screen. (Urine pregnancy test, U/A, and urine drug screen will be obtained from last visit of the previous NKTR-118 study)
- Daily maintenance and breakthrough pain opioid dosing regimens will be asked about and recorded on the appropriate eCRFs. For patients who enter the study from a previous NKTR-118 study, the daily opioid and breakthrough pain dosing regimens will be confirmed by prescription or clearly labeled bottles of opioid medication. If a patient forgets to bring their medication prescription/bottle(s) to Visit R1, they will be asked to bring it to Visit R2.
- Laxative medication will be asked about and recorded on the laxative medication eCRF. (For NKTR-118 patients, bisacodyl use will be captured on the bisacodyl drug accountability eCRF).

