- Use of concomitant medication (other than laxative or opioid medication) since Visit S2 will be recorded for new patients. Concomitant medications (other than laxative or opioid medication) ongoing at the end of the previous NKTR-118 study will be recorded for rollover patients.
- C-SSRS to assess suicidal risk, ideation, and behavior
- AEs since Visit S2 for new patients will be recorded. For rollover patients, AEs ongoing at the end of the previous NKTR-118 study, as well as resolved AEs meeting medical history criteria, will be recorded as new medical history.

- Modified Himmelsbach scale will be completed by the investigator before the patient receives the dose of study drug (obtained from last visit of the previous NKTR-118 study for rollover patients).
- I/E criteria will be reviewed with the patient.
- Patients who continue to meet I/E criteria (including confirmation of stability of the dose of the opioid) and new patients who also meet OIC criteria will be randomized to a treatment arm using the Interactive Voice Response System (IVRS).
- Unused bisacodyl will be returned (new patients).
- Blood samples will be collected for laboratory assessments (clinical chemistry [including total cholesterol] and hematology) (obtained from last visit of the previous NKTR-118 study for rollover patients).
- Blood sample will be collected for genetic sampling (if genetic informed consent signed). It is preferred that the blood sample for genetic analysis be collected at Visit R1; however, it may be collected at any visit during the study after the patient is randomized.

Dose/Meeting with Investigator:

- For patients randomized to NKTR-118, the first dose of open-label study drug will be administered at the study center and the patient observed for at least 4 hours. The accurate morning dose time in date, hours, and minutes will be recorded. Patients randomized to NKTR-118 will remain at the study center for additional post-dose assessments.
- Patients randomized to Usual Care will meet with the investigator to determine their OIC treatment regimen which will start the same day. Patients randomized to Usual Care will remain at the study center for at least 4 hours and will undergo the same additional assessments as patients in the NKTR-118 group.

Post dose/Additional Assessments:

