- ^o The NRS will be collected in the eDiary for Visits S1 and S2. Starting with Visit R1 the NRS will be completed in the clinic. The NRS is to be completed at the start of the relevant visits prior to any investigations or discussions about symptoms with study staff. An exception to this is made for Visit R1, since only randomized patients will fill out the questionnaires and interaction with study staff will be necessary to determine whether randomization criteria have been met. As applicable, the OIC Healthcare Resource Utilization Assessment is to be completed after the NRS, and prior to any investigations or discussions about symptoms with study staff.
- ^p For new patients who fail initial screening, AEs will be collected at Visit S2. For new patients who fail OIC confirmation, AEs will be collected at Visit R1.
- ^q Patients assigned to NKTR-118 will be asked to bring the study drug with them to each visit (to assess compliance); unused study drug will be returned/collected at each visit from M1 through M12.
- ^r Starting with Visit R1 bisacodyl will only be dispensed to NKTR-118 patients. Starting with Visit R2, bisacodyl will only be returned by NKTR-118 patients.
- ^s New patients only. (All new patients will return unused bisacodyl at randomization, irrespective of which treatment group they are assigned to).
- ^t Electronic diary assessments collected by new patients daily during screening and OIC-confirmation. eDiary pilot training will begin at Visit S1.
- ^u New patients who do not meet initial screening criteria will return the eDiary device at Visit S2; remaining new patients will return the eDiary device at Visit R1.

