5.4 Blinding and procedures for unblinding the study

Since this is an open-label study no procedures for blinding or unblinding are applicable.

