6.3.7 NRS for pain

Pain intensity is commonly evaluated via single-item measures that require patients to provide a quantifiable categorical and/or numerical rating of their pain. The most evaluated measures of pain intensity include NRS and visual analogue scales; both have been shown to demonstrate excellent psychometric characteristics across a wide range of clinical trial environments. The 11-point NRS has been recommended as the preferred response format for

use in clinical trials ([Dworkin et al 2005](#)). The NRS rates pain from 0 (no pain) to 10 (worst pain imaginable). Changes in this scale should generally not be reported as AEs unless standard criteria for AE reporting are otherwise met.

For new patients, during the OIC confirmation period the NRS will be recorded each evening via the eDiary to record the patients' worst pain and average pain during the day. For all randomized patients, patients will be asked to complete the NRS question on paper form at relevant study visits indicating their average pain during the 7 days prior to the visit. Patients are to fill out the questionnaire in a quiet area, without any help from family, friends, or study staff. With the exception of Visit R1, where some interaction with staff will be necessary in order to ensure that randomization criteria have been met, patients are to fill out the NRS prior to any interventions or discussions regarding their OIC with the study staff or the investigator.

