11.1.2 NRS for pain

The 11-point NRS for pain ranging from 0 (no pain) to 10 (worst imaginable pain) will be reported based on the average pain experienced during the 7 days before the study visit. Change from baseline in average NRS values will be calculated for Weeks 1 and 2, Months 1, 2, 3, 6, 9, and 12 as the post-baseline value minus the baseline value. Negative changes from baseline indicate improvement.

For all patients, the NRS (7-Day recall) collected at Visit R1 will serve as the NRS baseline value.

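### The protocol contradicts itself on whether the Visit R1 pain score, the only baseline for NRS change, is rated before or after randomization in this open-label trial

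*Protocol*

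**What the plan says.** Baseline. Protocol Section 11.1.2 states: "For all patients, the NRS (7-Day recall) collected at Visit R1 will serve as the NRS baseline value". Change is computed "as the post-baseline value minus the baseline value" at Weeks 1 and 2 and Months 1, 2, 3, 6, 9 and 12. Section 12.2.1 summarizes observed scores and changes by treatment group.

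Order at R1, visit list. Section 3.1.2.1 includes this item among the pre-dose/initial assessments: "Pain level question (NRS) (average pain over the previous 7 days) will be completed". The eligibility review and the IVRS randomization step come later in the same list.

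Order at R1, questionnaire rules. Section 6.4.2 requires the form at the start of each later visit, before any discussion of symptoms, but exempts the randomization visit "since only randomized patients will fill out the questionnaire" and because staff must first establish whether randomization criteria are met. Table 1 footnote o repeats this: "An exception to this is made for Visit R1, since only randomized patients will fill out the questionnaires". Section 6.3.7 makes the same exemption but gives only the eligibility reason: "With the exception of Visit R1, where some interaction with staff will be necessary in order to ensure that randomization criteria have been met".

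Blinding. Section 5.4: "Since this is an open-label study no procedures for blinding or unblinding are applicable".

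**The concern.** A baseline for a between-arm comparison should be measured before the arm is known. Restricting the R1 form to randomized patients is most easily done by waiting until randomization has happened. In this trial the patient can learn the arm at that moment, and on the same day either takes the first NKTR-118 tablet or discusses a laxative regimen with the investigator. Someone who has just learned the allocation may rate the past week's pain differently through hope or disappointment, and not equally in the two arms.

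The score matters because Section 3.2 relies on the NRS, together with opioid dose, to assess pain in patients given an opioid antagonist, and Section 6.3.1 lists NRS change as a safety variable. A baseline pushed upward on NKTR-118 would make later pain look improved and could hide some loss of analgesia; a downward push would do the reverse. Sites that read different sections could also collect the baseline at different moments.

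**Working it through.** The protocol states no figure that depends on this timing, so there is none to reproduce. The check sets the sections side by side and then follows the algebra.

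1. **Is R1 the only baseline?** Yes. Section 11.1.2 names it for all patients. Most other safety variables use an earlier pivotal-study baseline for rollover patients; the NRS does not.

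2. **Does the R1 list settle the order?** It points to pre-randomization: the NRS is listed ahead of the eligibility review and the IVRS step. The instruction to follow the listed order appears in the rollover paragraph of 3.1.2.1.

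3. **Does the list's heading settle it?** No. It guarantees pre-dose, not pre-randomization. The IVRS step is inside that list, and so is the genetic blood sample, which Section 6.8.1 takes after randomization. A form completed after the IVRS call would still be pre-dose.

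4. **Do 6.4.2 and footnote o agree with the list?** Not on their natural reading. They limit the form to randomized patients and place the eligibility discussion before it, whereas the list puts the form before the eligibility review.

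5. **Does any section require the score before disclosure?** None does.

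6. **Effect on the result.** Write P for the mean post-baseline score, B for the mean baseline without knowledge of the arm, and e for the mean shift in the R1 rating caused by that knowledge, with subscripts N (NKTR-118) and U (Usual Care). The observed difference in mean change is

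 (P_N - B_N - e_N) - (P_U - B_U - e_U) = (P_N - P_U) - (B_N - B_U) - d, where d = e_N - e_U.

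 The same baseline is subtracted each time, so the -d term enters at all 2 + 6 = 8 time points (two weekly, six monthly). If only a fraction f of patients in each arm rate after disclosure, and the shift among them is d, the term is -f × d. The documents give neither d nor f.

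7. **Is there a pre-randomization check?** In part. Under Section 6.2.2 new patients record average and worst pain each evening up to R1. Averaging the last seven daily average-pain ratings gives an arm-naive comparison, though not with the same instrument. Rollover patients keep no eDiary in this study. Section 3.1.2.1 lists an NRS at their last visit in the previous study, which coincides with R1, but does not give its recall period.

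**The case against.** The strongest reply is that the step-by-step procedure for R1 already has the score before allocation. On this view the exemption in 6.4.2 and footnote o only explains why an eligibility conversation may come before the form. Its second half speaks of determining whether randomization criteria are met, 6.3.7 gives that reason alone, and randomized may loosely mean found eligible. This stands as far as it goes. A reader might infer that sites must call the IVRS before giving the form; the documents do not say so. They permit that order without requiring it.

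A reader might also infer that no other pre-randomization 7-day score exists and that any damage could not be repaired. The first is unverified for rollover patients. The second overlooks the daily ratings of new patients and the observed scores by arm, which need no baseline. These are partial checks, not replacements for the specified change variable.

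It is also fair to say that every later NRS score is rated with the arm known. A reporting effect present at both times would partly cancel in the change, so -d is the baseline's contribution and not necessarily the net bias.

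Finally, no statistical testing is planned (Section 12.2), and the NRS is one of several descriptive safety variables. That lowers the severity but does not remove the contradiction: the secondary objective is a descriptive comparison of the arms, which a differential baseline would distort.

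**Conclusion.** The contradiction is real and should be fixed. What is established is that the protocol gives conflicting instructions on the timing of the sole NRS baseline, and that one set of them allows it to be rated with the arm known. It is not established that any site would do so or that ratings would move.

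The size is -d, or -f × d under mixed practice, at each of the eight time points, with d and f unknown. Scaling by a standard error is tempting but settles little. With an assumed SD of 2 points and all 1135 patients split 2:1 (about 757 and 378), SE = 2 × sqrt(1/757 + 1/378) = 0.126, and an assumed shift of 0.2 to 0.5 points would be about 1.6 to 4.0 SE. With the planned 125 NKTR-118 patients at 12 months and an assumed 63 on Usual Care, SE = 2 × sqrt(1/125 + 1/63) = 0.31, and the same shift is about 0.6 to 1.6 SE. The SD and the shift are not in the protocol, both ranges suppose that every patient rated after disclosure, and no test uses them. They do not support calling this critical.

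**What to change.** In Section 6.4.2 and Table 1 footnote o, replace the clause restricting the R1 form to randomized patients. In Section 6.3.7, which does not contain that clause, reword the R1 exception. All three should say that the 7-day NRS at R1 is completed after informed consent and before the IVRS assignment is obtained or disclosed, in the position it already holds in Section 3.1.2.1. Consent needs mentioning because rollover patients sign it at R1, before any study procedure; new patients have signed at S1. Add that scores from patients who are then not randomized are not used.

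The cost is a few sentences, a site instruction, and a one-item form completed by a few patients who then fail eligibility. No analysis changes.

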6.5 Efficacy (Not applicable)

6.6 Pharmacokinetics (Not applicable)

6.7 Pharmacodynamics (Not applicable)

6.8 Pharmacogenetics

See [Appendix D](#) for details on pharmacogenetic sampling.

6.8.1 Collection of pharmacogenetic samples

The blood sample for genetic research will be obtained from all patients post-randomization, even if collected in another NKTR-118 study. Although genotype is a stable parameter, early sample collection is preferred to avoid introducing bias through excluding patients who may discontinue due to an AE, such patients would be important to include in any genetic analysis. If for any reason the sample is not drawn at Visit R1 (randomization), it may be taken at any visit until the last study visit. Only 1 sample should be collected per patient for genetics during the study. Samples will be collected, labeled, stored, and shipped as detailed in the Laboratory Manual.

For blood volume, see Section [7.1](#).

6.9 Health economics

6.9.1 OIC Healthcare Resource Utilization Form

Opioid-induced constipation related healthcare resource utilization data will be collected at Week 1, Week 2, Months 1, 2, 3, 6, 9, 12, and at the follow-up visit through patient interviews. If a patient is taken off the study as a result of a resource utilization (eg, an ER visit for manual disimpaction), the data should be recorded in the OIC healthcare resource utilization form prior to discontinuation. A health care resource utilization form will be used to collect information on whether the patient had any contact or visited with a health care provider (physician or other health care practitioner, urgent care center or hospital emergency room, or inpatient hospital) for the management of their OIC, including the details of the type and number of visits, as well as the reason for the visit (such as the use of enemas, manual disimpaction, and treatment of anal fissures). As applicable, the interview will be conducted after the patient completes filling out the PRO questionnaire (NRS), and prior to any other interventions or discussions regarding the patient's OIC with the study staff or the investigator.

The PI must report medication use reported on the OIC Healthcare Resource Utilization Form (eg, enemas) on the laxative medication eCRF. The OIC Healthcare Resource Utilization Form should not be used to report AEs but they should be reported on the AE eCRF.

7. BIOLOGICAL SAMPLING PROCEDURES

7.1 Volume of blood

The total volume of blood that will be drawn from each patient in this study is as follows:

Table 3 Volume of blood to be drawn from each patient

Assessment		Sample volume (mL)	No. of samples	Total volume (mL)
Safety	Clinical chemistry ^a	8.5 SST	10	85
	Hematology	4 EDTA	10	40
	Bicarbonate	3.5 SST	10	35
	Coagulation (PT/INR)	4.5 Sodium Citrate	1	4.5
Pharmacogenetics		10 EDTA	1	10
Total		30.5	32	174.5

EDTA Ethylenediaminetetraacetic acid, SST serum-separating tube

^a Additional samples may be collected for patients who have elevated liver transaminases (see Section 6.3.9.2), who require repeat laboratory testing at screening, or who require a serum pregnancy test.

Urine samples will be taken from each patient for the purpose of drug screening and U/A. Urine samples from WOCBP will be used to test for pregnancy at selected visits.

7.2 Handling, storage and destruction of biological samples

The samples will be used up, disposed of after analyses, or retained for further use as described here.

The laboratory will provide detailed instructions of all laboratory procedures, handling, and shipment of laboratory samples before the study start. The samples should be properly taken, handled, labeled, and shipped in accordance with the instructions provided by the laboratory. Samples should be shipped to the laboratory by courier unless otherwise agreed.

The analyte stability limits defined by the laboratory will be applied to all analyses performed on behalf of AstraZeneca. The laboratory will not analyze samples that fall outside these stability limits. Analytical data found to have been derived from a sample that fell outside these stability limits would not be reported. The standards of procedures followed by the laboratory may be amended in accordance with their SOPs. The laboratory will inform AstraZeneca or its representative of the stability limits relevant to this study before the first patient gives informed consent to take part in the study.

